AE: adverse event; ctDNA: circulating tumor DNA; ECG: electrocardiogram; ECOG: Eastern Cooperative Oncology Group; ELISpot: enzyme-linked immunospot; EOT: end of treatment; iCPD: “immune” confirmed progressive disease; iUPD: unconfirmed disease progression disease based on iRECIST; SAE: serious adverse event; WOCBP: woman of childbearing potential; WT1: Wilms’ tumor 1 protein.

Footnotes continued on next page

- a. For participants in ASP7517 monotherapy treatment arm. Participants in the Observation period will be followed until iCPD, iUPD who are not clinically stable, clinical disease progression, initiation of a new anticancer therapy or for a total of up to 48 weeks starting at EOT, whichever occurs first.
- b. Maximum of 8 samples collected during the Observation Period. Sample will be collected at the time of the disease assessment visit.
- c. Maximum of 4 samples collected during the Observation Period. Sample will be collected at the time of the disease assessment visit.
- d. Sample will be collected only at the time of discontinuation due to disease progression.
- e. Outcomes will be assessed by telephone calls every 3 months for up to 12 months.
- f. In Monotherapy Arm, Safety Follow-up is a part of 48 weeks of Observation period. Observation period starts after EOT.

Table 4 Schedule of Assessments for Observation Period, Safety Follow-up and Survival Follow-up for Participants who Receive Pembrolizumab Monotherapy in the Observation Period

Visit	Observation Period Up to 96 weeks ^a	Safety Follow-up			Survival Follow-up
	Visits every 6 weeks (\pm 1 week) from last Pembrolizumab dose during combination treatment	30 days from last dose	60 days from last dose	90 days from last dose	Every 3 months
Window (days)		\pm 3	\pm 3	\pm 3	\pm 7
Physical Examination	X	X	X	X	
Vital Signs	X ^b	X	X	X	
ECOG Performance		X	X	X	
Concomitant Medications	X	X	X	X	
12-Lead ECG	X ^c	X	X	X	
Clinical Laboratory Tests (chemistry, hematology, coagulation, urinalysis)	X ^c	X	X	X	
Thyroid Profile Panel (triiodothyronine or free triiodothyronine, free thyroxine and thyroid stimulating hormone)	X ^c	X ^c			
Pregnancy Test for WOCBP	X ^c	X	X	X	
AE/SAE Assessment	X	X	X	X	
Pharmacokinetic samples for cell kinetics (ASP7517)	See Table 6 for schedule				
Pharmacokinetic sample for pembrolizumab	See Table 6 for schedule				
Blood Sample for anti-WT1 antibody	X ^{c,h}				
Blood Sample for Immune Response Biomarker (ELISpot)	X ^{c,g}				

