5.1.2.5 Progression-free Survival per iRECIST (iPFS)

iPFS is defined as the time from the start of the study treatment until death from any cause or radiographic disease progression assessed per iRECIST by investigator assessment, whichever occurs first.

If iUPD occurs but iSD, iPR, or iCR is observed any time subsequent to iUPD, iUPD status will be disregarded for determination of iPFS.

Table 2 iPFS Definition

iPFS		
Situation	Date of Event or Censor	Outcome
No evaluable post-baseline imaging assessments, no death	Date of first dose (Day 1)	Censor
Participant did not receive new anti-cancer therapy:		
iCPD	First date where iUPD criteria are met	Event
No iCPD, but death recorded on eCRF	Date of death	Event
No iCPD nor death and not in one of the following cases :a)if the participant stops protocol treatment because they were not judged to be clinically stable, b) no further response assessments are done (because of participant refusal, protocol non-compliance, or participant death); c) the	Date of last radiological assessment	Censor

iPFS		
Situation	Date of Event or Censor	Outcome
next timepoint responses are all iUPD, and iCPD never occurs;		
No iCPD nor death and is in one of the following cases : a)if the participant stops protocol treatment because they were not judged to be clinically stable, b) no further response assessments are done (because of participant refusal, protocol non-compliance, or participant death); c) the next timepoint responses are all iUPD, and iCPD never occurs;	First date where iUPD criteria are met	Event
Participant received new anti-cancer (ACT) therapy:		
No progression before new ACT	Date of last radiological assessment before start of new anti-cancer therapy	Censor
iCPD before new ACT	First date where iUPD criteria are met	Event
iUPD before new ACT and not in one of the following cases : a)if the participant stops protocol treatment because they were not judged to be clinically stable, b) no further response assessments are done (because of participant refusal, protocol non-compliance, or participant death); c) the next timepoint responses are all iUPD, and iCPD never occurs;	Date of last radiological assessment before start of new anti-cancer therapy	Censor

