iUPD before new ACT and is in one of the following cases : a)if the participant stops protocol treatment because they were not judged to be clinically stable, b) no further response assessments are done (because of participant refusal, protocol non-compliance, or participant death); c) the next timepoint responses are all iUPD, and iCPD never occurs;	First date where iUPD criteria are met	Event
Missed ≥ 2 scheduled radiological assessments		
If last assessment prior to missing ≥ 2 scans is iUPD	First date where iUPD criteria are met	Event
If last assessment prior to missing ≥ 2 scans is not iUPD and no progression or death after missing ≥ 2 scans	Date of last radiological assessment	Censor

iPFS		
Situation	Date of Event or Censor	Outcome
No post-baseline tumor imaging prior to missing 2 scans and progression or death after missing ≥ 2 scans	Date of first dose (Day 1)	Censor
No post-baseline tumor imaging prior to missing 2 scans and no progression or death after missing ≥ 2 scans	Date of last radiological assessment	Censor
If radiographical progression or death occurs after missing 2 scheduled radiological assessments and last assessment prior to missing ≥ 2 scans is not iUPD	Date of last radiological assessment before missing 2 scans	Censor

iPFS = Date of Event or Censor – Date of First Dose +1

Missing 2 scheduled imaging assessments:

Missing 2 scheduled imaging assessments is defined as the gap between two imaging assessments being more than 140 days (2.5 times the scheduled imaging assessment interval (2.5 x 56 days)). Imaging assessments after first iUPD will be excluded from PFS derivation.

Note: Participant cannot be censored at “NE”. If NE is the only previous assessment, then iPFS will be censored at Day 1.

To apply the cut-off date to iPFS is to exclude those tumor assessments after cut-off date and anti-cancer therapy date after cut-off date in the analysis.

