5.1.2.6 Progression-free Survival per RECIST v1.1 (PFS)

PFS is defined as the time from the start of the study treatment until death from any cause or radiographic disease progression assessed per RECIST v1.1 by investigator assessment, whichever occurs first.

Table 3 PFS Definition

PFS		
Situation	Date of Event or Censor	Outcome
No evaluable post-baseline imaging assessments, no death	Date of first dose (Day 1)	Censor
Participant did not receive new anti-cancer therapy:		
Radiographical progression documented per RECIST v1.1	Date of radiological disease progression	Event

PFS		
Situation	Date of Event or Censor	Outcome
No radiographical progression, but death recorded on eCRF	Date of death	Event
Neither radiographical progression nor death	Date of last disease assessment	Censor
Participant received new anti-cancer (ACT) therapy:		
Radiographical progression documented per RECIST v1.1 after new ACT	Date of last radiological assessment before start of new anti-cancer therapy	Censor
Radiographical progression documented per RECIST v1.1 before new ACT	Date of radiological disease progression	Event
No radiographical progression before new ACT but death recorded	Date of last radiological assessment before start of new anti-cancer therapy	Censor
No radiographical disease progression nor death	Date of last radiological assessment before start of new anti-cancer therapy	Censor
Missed >=2 scheduled radiological assessments		
If radiographical progression or death occurs after missing 2 scheduled radiological assessments	Date of last radiological assessment before missing 2 scans	Censor

PFS = Date of Event or Censor – Date of First Dose +1

Missing 2 scheduled imaging assessments:

Missing 2 scheduled imaging assessments is defined as the gap between two imaging assessments being more than 140 days (2.5 times the scheduled imaging assessment interval (2.5 x 56 days)). Imaging assessments after first iUPD will be excluded in PFS derivation.

Note: Participant cannot be censored at “NE”. If NE is the only previous assessment, then PFS will be censored at Day 1.

To apply the cut-off date to PFS is to exclude those tumor assessments after cut-off date and anti-cancer therapy date after cut-off date in the analysis.

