5.1.2.7 Duration of Response per iRECIST (iDOR)

iDOR is defined as the time from the date of the first response iCR/iPR (whichever is first recorded) to the date of radiographical progression or date of censoring. iDOR will be

calculated only for the subgroup of participants with confirmed response iCR/iPR per iRECIST separately for investigator assessment.

Table 4 iDOR Definition

iDOR		
Situation	Date of Event or Censor	Outcome
Participant did not receive new anti-cancer therapy		
iCPD	First date where iUPD criteria are met	Event
No iCPD nor death and NOT in one of the following cases : a) the participant stops protocol treatment because they were not judged to be clinically stable, b) no further response assessments are done (because of participant refusal, protocol non-compliance, or participant death); c) the next timepoint responses are all iUPD, and iCPD never occurs;	Date of last radiological assessment	Censor
No iCPD nor death and is in one of the following cases : a) the participant stops protocol treatment because they were not judged to be clinically stable, b) no further response assessments are done (because of participant refusal, protocol non-compliance, or participant death); c) the next timepoint responses are all iUPD, and iCPD never occurs;	First date where iUPD criteria are met	Event
Participant received new anti-cancer therapy		
No progression before new ACT	Date of last radiological assessment before start of new ACT	Censor
iCPD before new ACT	First date where iUPD criteria are met	Event
iUPD before new ACT and NOT in one of the following cases : a) the participant stops protocol treatment because they were not judged to be clinically stable, b) no further response assessments are done (because of participant refusal, protocol non-compliance, or participant death); c) the next timepoint responses are all iUPD, and iCPD never occurs;	Date of last radiological assessment before start of new ACT	Censor

iDOR		
Situation	Date of Event or Censor	Outcome
Participant did not receive new anti-cancer therapy		
iUPD before new ACT and is in one of the following cases : a) the participant stops protocol treatment because they were not judged to be clinically stable, b) no further response assessments are done (because of participant refusal, protocol non-compliance, or participant death); c) the next timepoint responses are all iUPD, and iCPD never occurs;	First date where iUPD criteria are met	Event

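### The iPFS rules censor, usually at the progression scan, participants outside cases a to c who start new therapy before iUPD is confirmed

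*SAP*

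**What the plan says.** SAP 5.1.2.5, Table 2, has two rows for a participant with iUPD, not yet confirmed, before new anticancer therapy (ACT).

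- **Event row:** "iUPD before new ACT and is in one of the following cases". The event is dated to the first iUPD. Case a is stopping protocol treatment because of clinical instability. Case b is "no further response assessments are done (because of participant refusal, protocol non-compliance, or participant death". Case c is that every later timepoint is iUPD and confirmed progression (iCPD) is never reached.
- **Censor row:** "iUPD before new ACT and not in one of the following cases". The censor date is "Date of last radiological assessment before start of new anti-cancer therapy".

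A separate row makes iCPD before new ACT an event, also dated to the first iUPD. A rule above the table adds that if iSD, iPR or iCR "is observed any time subsequent to iUPD, iUPD status will be disregarded for determination of iPFS".

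SAP 5.1.2.7, Table 4, repeats the pair of rows for iDOR ("iUPD before new ACT and NOT in one of the following cases"). For RECIST v1.1 PFS, SAP Table 3 lists "Radiographical progression documented per RECIST v1.1 before new ACT" as an event at the progression date.

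Protocol 7.1 places the confirmatory scan 4 to 8 weeks after first progression and continues 8-weekly imaging until iCPD. Protocol Table 3, footnote a, ends the monotherapy observation period at the earliest of several events, including "initiation of a new anticancer therapy or for a total of up to 48 weeks starting at EOT". Protocol Table 4, footnote a, also names new anticancer therapy for the combination arm.

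**The concern.** A participant can progress, remain clinically stable and change therapy before the confirmatory scan. Protocol 8.1 makes progression a reason to stop study treatment without asking about clinical stability, so stopping for progression is not in itself case a. New therapy is not among the reasons given in case b. On the wording, this participant goes to the censor row, and the last scan before the switch is the one that showed progression.

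The participant then leaves the iPFS risk set because of progression. Such censoring is likely to be informative, and it pushes the Kaplan-Meier curve upward. SAP 6.4.2.5 and 6.4.2.6 summarise iPFS and PFS side by side. A gap produced by this row could be misread as late immune benefit.

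**Working it through.** **No design figure to reproduce.** The documents give no expected median, event count or power for iPFS or iDOR. The one related calculation, the missed-scan gap of 2.5 × 56 = 140 days, is correct.

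**Step 1. Run each type of participant with iUPD and new ACT through Table 2.**

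| Course after iUPD | Result in Table 2 |
|---|---|
| A. Stopped as not clinically stable, then ACT | Event at first iUPD (case a) |
| B. No further scans: refusal, non-compliance or death | Event at first iUPD (case b) |
| C. Only iUPD afterwards, never iCPD | Event at first iUPD (case c) |
| D. iSD, iPR or iCR before the switch | Censored at a later non-progression scan, which is coherent |
| E. Stable, switches before confirmation, scans stop because of ACT | Censored at the iUPD scan if case b is a closed list; event if any absence of scans counts |
| F. Stable, switches, iCPD on a scan after ACT | Censored at the iUPD scan on both readings of case b |
| G. Stable, switches, iSD, iPR or iCR on the new drug | The disregard rule has no limit at ACT, so the iUPD can be cancelled; censored at the iUPD scan |

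E arises if imaging ends at new therapy. F and G arise if it continues until iCPD, as Protocol 7.1 says. The documents leave room for both.

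**Step 2. Compare with the SAP's other rows.**

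- In F, progression is confirmed. Table 2 dates an iCPD event to the first iUPD, which precedes the switch, yet this participant is censored.
- Table 2 counts an event at first iUPD when iUPD is the last scan before two or more missed scans, without asking why they were missed. That row does not clearly rescue E: the gap is defined between two scans, and E has no later one.
- SAP Table 3 counts progression before new ACT as an event, with no condition on confirmation.

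**Step 3. Size, for illustration.** Let h be the true hazard, m = ln 2/h the true median, and f the share of progressions censored at the progression date, taken as a random share. The apparent hazard is (1-f)h, so the apparent median is m/(1-f). Survival at time t becomes S(t)^(1-f). Both f and m are assumptions.

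| f | 1/(1-f) | Median if m = 56 days | Median if m = 112 days | 168-day iPFS if m = 112 days |
|---|---|---|---|---|
| 0 | 1.00 | 56.0 | 112.0 | 0.354 |
| 0.05 | 1.05 | 58.9 | 117.9 | 0.372 |
| 0.10 | 1.11 | 62.2 | 124.4 | 0.392 |
| 0.20 | 1.25 | 70.0 | 140.0 | 0.435 |

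For example, 2^(-168/112) = 0.354 and 0.354^0.8 = 0.435. Simulation of 20,000 participants with m = 112 gave medians of 116.5, 124.1 and 141.0 days for the last three rows, in line with the formula.

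Deaths without progression are also iPFS events. If progression makes up a share p of events, the apparent hazard is (1-fp)h, so the table is the upper end for a given f.

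**The case against.** The strongest reply is that the residual group is small. Cases a to c and iCPD before ACT are all events, so courses A to C are handled properly, and D is censored for good reason. Participants with iUPD who are not clinically stable are kept out of the observation period and, if treatment stopped for that reason, fall under case a. Apart from CPI-naïve melanoma in phase 2, participants must have had all appropriate standard therapies unless contraindicated or intolerable (Protocol 5.1), so a quick switch is not to be presumed. This stands: the documents do not show how often E, F or G would occur.

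Case b might also be read broadly, so that any absence of later scans counts. That would make E an event but leave F censored. Case c might be said to hold trivially when no later scan exists, but case b would then be redundant.

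A note under Table 2 drops imaging after the first iUPD from the PFS derivation. If it governs iPFS, course G falls away. It would then also conflict with the disregard rule, with case c and with the use of a later scan to establish iCPD. The note shows that the section needs reconciling; it does not settle the classification.

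Finally, iPFS is descriptive. The hypotheses and stopping boundaries use iORR, RECIST v1.1 PFS is shown alongside, and iPFS is listed by participant. This stands and lowers the priority.

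**Conclusion.** The point holds in a limited form. Table 2 censors F on both readings of case b, censors E on the literal reading, and lets a response to the new drug cancel an earlier iUPD. Kaplan-Meier iPFS is biased upward to the extent such participants exist. Under the stated assumptions (exponential times, random share f, progression as the only event) the median is inflated by 1.05, 1.11 or 1.25 times at f = 5%, 10% or 20%. At f = 0 there is no bias.

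A reader might infer more, but the documents do not support it:

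- **That every iUPD followed by new therapy is censored.** The event row covers cases a to c.
- **That iPFS is overstated, or exceeds PFS by construction.** That needs participants in E to G, whose number is unknown. The disregard rule already lets iPFS exceed PFS by design, so a gap alone proves nothing.
- **That f is large.** The relevant f excludes unstable participants, who are events under case a, so it is not the share of all progressors who switch early.
- **That duration of response is inflated.** SAP 6.4.2.7 only lists iDOR, so the effect is a wrong event or censor status in a listing.

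No error rate, sample size or decision rule depends on iPFS. The correction is worthwhile but is not a condition for the main analysis.

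**What to change.** In SAP Tables 2 and 4:

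1. Use only scans up to the start of new anticancer therapy.
2. If an iUPD was not followed by iSD, iPR or iCR before the new therapy, count an event at the first date of that iUPD, whatever the reason for the missing confirmatory scan. This replaces the residual censor row.
3. Limit the disregard rule to scans before new therapy.
4. Reconcile these rules with the note that drops imaging after the first iUPD, stating whether it applies to iPFS and iDOR or only to the RECIST v1.1 endpoints.

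The cost is revised wording and a small derivation change, with no new data. iPFS may become slightly less favourable.

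### The SAP 5.1.2.5 note dropping scans after the first iUPD is not limited in scope; applied to iPFS, it defeats the iUPD-disregard rule and the iCPD rows

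*SAP*

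**What the plan says.** SAP 5.1.2.5 states a general rule ahead of Table 2: "If iUPD occurs but iSD, iPR, or iCR is observed any time subsequent to iUPD, iUPD status will be disregarded for determination of iPFS". The rows below it then make iCPD an event, dated back to the first iUPD. Without iCPD or death, an iUPD still counts as an event in three cases: (a) treatment stopped because the participant was not clinically stable; (b) no further response assessments were done; (c) "the next timepoint responses are all iUPD, and iCPD never occurs". A separate row, "No iCPD, but death recorded on eCRF", is an event at the date of death. Among the missed-scan rows, "If last assessment prior to missing ≥ 2 scans is iUPD" gives an event at the first iUPD.

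Under the table, the paragraph that defines two missed scans as a gap of more than 140 days ends with "Imaging assessments after first iUPD will be excluded from PFS derivation". The next note names the other endpoint: "If NE is the only previous assessment, then iPFS will be censored at Day 1".

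The RECIST v1.1 section (5.1.2.6) has its own copy: "Imaging assessments after first iUPD will be excluded in PFS derivation". The iDOR section (5.1.2.7) carries a parallel sentence for DOR. The RECIST v1.1 DOR section (5.1.2.8) has none.

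Protocol 7.1 schedules imaging every 8 weeks until iCPD and asks for the confirmatory progression scan 4 to 8 weeks after the first one. SAP 6.4.2.5 still plans a Kaplan-Meier summary of iPFS after the version 2.0 cutback.

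**The concern.** A scan taken after an iUPD cannot both cancel that iUPD and be left out of the derivation. The iCPD rows and case (c) have the same dependency, since both are defined by what later scans show. If the note governs iPFS, three parts of the section's own logic have no data to work on, and iPFS loses the confirmation step that separates it from RECIST v1.1 PFS. Two programmers following the SAP in good faith could then give the same participant different dates or outcomes, in groups that are small because SAP 6.4 summarizes efficacy by dose level, phase and tumor type.

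**Working it through.** **Inputs.** Scan interval 56 days (Protocol 7.1; SAP 5.1.2.5). Event and censoring rules from SAP Table 2, the block without new anti-cancer therapy. The participants are hypothetical, because the documents give no data on such cases.

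**The plan's own figure.** 2.5 × 56 = 140 days, which reproduces the missed-scan threshold.

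**The same participants under two readings of the note.**

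| Participant | Scan history | All scans used | Note applied to iPFS | Difference in date |
|---|---|---|---|---|
| A: progression later reversed | iUPD Day 57, iPR Day 113, responding to Day 337 | Censored Day 337 | Event or censor Day 57 | 337 − 57 = 280 days |
| B: progression confirmed, then death | iUPD Day 57, iCPD Day 113, death Day 141 | Event Day 57 (iCPD row) | Event Day 141 (death row) | 141 − 57 = 84 days |
| C: reversed, then true progression | iUPD Day 57, iPR Day 113, iUPD Day 169, iCPD Day 201 | Event Day 169 | Day 57 (event if case (b) is applied) | 169 − 57 = 112 days |
| D: progression confirmed, no death | iUPD Day 57, iCPD Day 113 | Event Day 57 | Day 57 (event if case (b) is applied) | 0 days |

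- In A, the outcome under the note is itself not fixed. Case (b) lists refusal, non-compliance or death as reasons for having no further assessments. It does not say whether scans that exist but are excluded count. If they do, A is an event at Day 57; if not, A is censored at the last retained scan, also Day 57.
- In B, removing the Day 113 scan removes iCPD. The rows that require neither iCPD nor death do not apply, which leaves the death row. The 84 days from the last retained scan to death are below 140, so no missed-scan row intervenes. The result is the same if iCPD falls on Day 85.
- D shows where the note does not move the date.

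**Size on the Kaplan-Meier curve.** If A is counted as an event at Day 57 and nobody has been censored earlier, the Day 57 estimate falls by 1/n. Protocol 4.1.5.2 gives 3 to 12 participants in the dose escalation cohort: 1/3 = 33.3 points, 1/6 = 16.7 points, 1/12 = 8.3 points. If A is censored at Day 57 instead, that estimate does not fall; 280 days of event-free follow-up are lost.

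**Missed-scan row, a separate matter.** Take iUPD on Day 57, two scans missed, and iSD on Day 225. The gap is 225 − 57 = 168 days, above 140. The missed-scan row read alone gives an event at Day 57. The disregard rule gives no event and censoring at Day 225 or later, at least 168 days apart.

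**The case against.** The best defence is that the sentence does not concern iPFS at all. It says PFS, the SAP uses iPFS and PFS as separate names, and the note beside it says iPFS. The iDOR section supports this: its notes name both DOR and iDOR where both are meant, yet its exclusion sentence names DOR alone. A second defence is position: the sentence closes the paragraph on missed scans and could be meant only for the gap calculation. A third is that a reading which empties several table rows is the one least likely to be programmed.

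These points stand as plausible readings, and they lower the certainty of harm. They do not remove the defect. Neither limit is written, and the sentence speaks of the derivation, not of the gap. If it was meant for RECIST v1.1 PFS, 5.1.2.6 already has it, so its place among the iPFS rules is still wrong.

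On the missed-scan row, the defence is stronger. The disregard rule stands before the whole table, applies at any later time and has no exception for a gap. A later iSD therefore removes the iUPD status on which that row depends. The example also needs a long gap after an iUPD, although the protocol asks for a confirmatory scan within 8 weeks.

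**Conclusion.** The defect is real but modest: an unrestricted sentence sits among the iPFS rules and, applied to iPFS, contradicts them. On that reading iCPD cannot be reached, a reversed progression becomes an event or a censor at the first iUPD, and a confirmed progression followed by death moves to the death date. Where an iUPD is confirmed or never resolved and no death follows, the date does not change.

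Three stronger conclusions might be inferred, and the documents do not support them.

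- That iPFS will in fact be derived wrongly. The note may well be a carry-over, and nothing shows how it was programmed.
- That the missed-scan row and the disregard rule are in open contradiction. The rule already reads as general; only an explicit confirmation is lacking.
- That the Day 57 estimate necessarily falls by 1/n. This holds only if the participant is counted as an event, not if censored.

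The consequence is bounded. iPFS is a secondary endpoint with a descriptive Kaplan-Meier summary, iDOR is only listed (SAP 6.4.2.7), and iORR does not use these rules. The frequency of such participants is unknown. The examples assume 56-day scans and no new anti-cancer therapy.

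**What to change.** - Delete the exclusion sentence from SAP 5.1.2.5, and the parallel sentence from iDOR in 5.1.2.7, where the iCPD row and case (c) also need later scans.
- Leave 5.1.2.6 as it is, since it has its own copy. Nothing needs to be moved into 5.1.2.8: Table 5 already dates RECIST v1.1 progression without reference to iUPD.
- As a secondary clarification, add one sentence to 5.1.2.5 confirming that the disregard rule also applies to the missed-scan iUPD row.

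The cost is SAP text and a check of the derivation program; no new data are needed. SAP section 1 has the final SAP approved before database hardlock and sends changes to planned analyses to the clinical study report. If the lock has passed, the report should state which rule was programmed.
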